^c Count recovery is defined as an absolute neutrophil count >1000/ μ L and a platelet count >100,000/ μ L. If count recovery occurs, perform bone marrow aspirate/biopsy within 7 days. If count recovery has not occurred by ~Day 36 after induction or reinduction, perform a bone marrow aspirate/biopsy on or before Day 42 to evaluate disease status.

^d Participants who do not achieve leukemia-free state (<5% bone marrow blasts) on bone marrow aspirate performed between ~Days 14-21 (Day 22-23 for participants taking midostaurin) may receive a reinduction cycle. Participants 18 to 59 years will receive the same 7+3 regimen; participants \geq 60 years will receive a modified “5+2” regimen, with cytarabine and study intervention administered on Days 1 through 5 and idarubicin/daunorubicin on Days 1 and 2.

^e Do not draw blood (especially for aPTT or PK analyses) from the same line that is used for study intervention administration. Drawing blood from a heparinized line may falsely alter results obtained; if using an indwelling catheter, draw ~5 mL of blood from the line for discard before drawing the aPTT and PK samples.

^f Draw blood for aPTT measurements no sooner than 8 hours after the bolus dose. During the continuous infusion, measure aPTT daily.

^g Refer to laboratory manual for instructions on obtaining a separate sample for HMGB1 analyses versus using a biobanked sample.

Note: All participants will be followed-up for long-term outcomes for 5 years after randomization. See Section [8.2.3](#).

Table 2: Schedule of Activities/Assessments: Consolidation Cycles

Study Day: Examination / Procedure	D1	D2	D3	D4	D5	D6	D14	D7 until count recovery or D42 ^h	Follow-up	Notes
Weight	X									Day is relative to start of each treatment cycle
Bone marrow aspirate/ biopsy:										After each consolidation cycle and to confirm response/ relapse/ persistent disease
–Morphology (local)								X – at recovery		
–MRD analyses (central)								X – at recovery		After each consolidation cycle
–Biobanking (central)								X – at recovery		Optional, per local regulations/approvals
Peripheral blood samples:										
–Hematology (local)	X	X		X		X	X	X		Every other day through recovery
–Clinical chemistry (local)	X	X		X		X	X			
–PT/INR, aPTT ^{i,j} (local)	X	X	X	X	X	X	X			
–HMGB1 ^{g,i} (central)	X							X – at recovery		
–Biobanking (central)								X – at recovery		

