6.6. Concomitant Therapy

Information about the participant's concomitant medications/therapies will be collected in the eCRF as specified below.

Collection time periods:

- Prior medications: All medications taken from 30 days prior to the time of signing the informed consent form (ICF) through the time of randomization.

- Concomitant medications: All medications and transfusions from the time of first dose of study intervention on Day 1 through 42 days after the start of the last treatment cycle (induction, reinduction, or consolidation, whichever is later).
- Follow-up: Only AML therapies (i.e., for the treatment of AML and/or prevention of relapse) from 43 days after start of last treatment cycle through the time of last study follow-up.

Information to collect:

- Names (nonproprietary names are preferred) for all prescription medications and growth factors, and details of transfusions (do not need to collect use of vitamins, supplements, or IV fluids).
- Reason for use (indication).
- Start and end dates of administration.
- Dosage information, including dose, units, route, and frequency.

Contact the medical monitor (or designee) if there are any questions regarding concomitant or prior therapy.

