6.6.2. Permitted Therapies

The following medications are permitted during the study:

- Midostaurin: Participants who are known to have a FLT3 mutation may, at the investigator's discretion and dependent on local availability, receive midostaurin in accordance with the product label.
- Infection prophylaxis and treatment, and transfusion support – according to institutional standard of care.
- Granulocyte colony-stimulating factor (G-CSF) following consolidation therapy.

If used, recommended treatment is a single dose (per package labeling) of peg-filgrastim/liposomal G-CSF (Neulasta or biosimilar) administered subcutaneously 24 to 48 hours after the last dose of cytarabine consolidation in participants who have achieved an MRD_{neg} CR or CRi after induction/reinduction. Alternatively, other G-CSF agents may be used after consolidation therapy per institutional standard of care and package labeling.

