8.2.2. Response Criteria and Outcome Measures

Response criteria and outcome measures (Table 7) are based on definitions from ELN (Döhner 2017).

Table 7: Response Criteria and Outcomes Measures

Response / Outcome	Definition
Response	Complete remission with complete hematologic recovery (CR) Defined for all study participants at the end of induction therapy. Bone marrow blasts <5%, absence of circulating blasts and blasts with Auer rods, absence of extramedullary disease, ANC >1.0 x 10 ⁹ /L (1000/µL), and platelet count >100 x 10 ⁹ /L (100,000/µL). Recovery of ANC and platelet counts within 7 days before or 7 days after bone marrow biopsy showing blasts <5% may be used to assess best response.
	CR with incomplete hematologic recovery (CRI) Defined for all study participants at the end of induction therapy. All CR criteria (bone marrow blasts <5%; absence of circulating blasts and blasts with Auer rods; absence of extramedullary disease), except for residual neutropenia ($\leq 1.0 \times 10^9/L$ [1000/µL]) or residual thrombocytopenia ($\leq 100 \times 10^9/L$ [100,000/µL]). [Note: Participants with both residual neutropenia and residual thrombocytopenia are not considered to have achieved CRI.]
	CR with partial hematologic recovery (CRh) Defined for all study participants at the end of induction therapy. CR criteria (bone marrow blasts <5%; absence of circulating blasts and blasts with Auer rods; absence of extramedullary disease), with partial recovery of peripheral blood counts (ANC >0.5 x 10 ⁹ /L [500/µL] and partial recovery of platelets >50 x 10 ⁹ /L [50,000/µL], but the count recovery criteria for CR are not met).

Response / Outcome	Definition
Measurable residual disease negative (MRD _{neg})	
Defined for all study participants at the end of induction and consolidation therapy.
 
Negative (undetectable) MRD in recovery (~Day 22-42) bone marrow, as measured by MFC (0.1% detection limit).

Failure (induction failure)	Failure to achieve CR (or CR/CRi) within 42 days of the start of induction therapy (or start of reinduction therapy when applicable).
Relapse (hematologic)	
Defined through 5 years after randomization only for participants achieving CR (or CR/CRi) during induction/reinduction.
 
After achievement of CR/CRi, bone marrow blasts $\geq 5\%$, reappearance of blasts in the blood, or development of extramedullary disease.

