Time to transfusion-independent platelet recovery	
Defined for all study participants.
 
Measured as time from date of randomization until the first day the platelet count recovers to $>20,000/\mu\text{L}$, $>50,000/\mu\text{L}$, and $>100,000/\mu\text{L}$, without a platelet transfusion in the preceding 5 days following induction or reinduction (if indicated).

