9.4.2. Key Secondary Endpoint

The key secondary EFS endpoint will be tested using the same method as the primary endpoint at two-sided alpha 0.01. A participant with any bone marrow CR assessment between Days 22 and 42, inclusive, after start of induction or reinduction treatment will be considered an induction success; relapse and death events will be assessed following the last CR assessment during this time period. A participant with no CR assessments during this window will be considered an induction failure and imputed as such at randomization. Participants with induction success and no observed relapse or death events will be censored at the time they were last known to be alive. Maximum neutrophil and platelet counts within 7 days before or after the bone marrow draw will be used to determine count recovery. The key secondary analysis will be supplemented by a planned sensitivity analysis (not subject to alpha control), in which participants progressing to hematopoietic cell transplant will be censored at the time of transplant. The key secondary analysis will be conducted at the same time as the final primary OS analysis.

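### CR in the key secondary EFS can rest on a recently transfused platelet count, because count recovery uses the window maximum with no transfusion condition

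*Combined protocol and SAP*

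**What the plan says.** **CR derivation.** Section 9.4.2 gives the rule for the key secondary EFS: "Maximum neutrophil and platelet counts within 7 days before or after the bone marrow draw will be used to determine count recovery". The CR row of Table 7 (Section 8.2.2) has the same allowance for judging best response: "Recovery of ANC and platelet counts within 7 days before or 7 days after bone marrow biopsy showing blasts <5% may be used". The platelet level for CR is above 100,000/µL. Neither place mentions transfusion. Nor do the count-recovery footnotes to Tables 1 and 2 or the CR entry in Appendix 7.

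**Platelet-recovery endpoint.** Table 7 and Appendix 7 define time to transfusion-independent platelet recovery at three levels, the highest being the CR level. A count qualifies only "without a platelet transfusion in the preceding 5 days following induction or reinduction (if indicated").

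**Supportive care and data.** Section 6.6.2 permits "Infection prophylaxis and treatment, and transfusion support" under institutional practice. Section 6.6 collects "All medications and transfusions from the time of first dose of study intervention on Day 1", ending 42 days after the start of the last treatment cycle. Section 6.6.1 prohibits growth factors during induction and reinduction.

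**Consequence of no CR.** Section 9.4.2: "A participant with no CR assessments during this window will be considered an induction failure and imputed as such at randomization".

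**The concern.** A maximum over repeated counts picks out the highest value, and a platelet count shortly after a transfusion is a candidate for that value. It reflects donor platelets, at least in part, and is weak evidence of marrow recovery. The protocol accepts this reasoning for its platelet-recovery endpoint but does not apply it to CR. The neutrophil half of count recovery is shielded, because growth factors are barred in the relevant cycles. The platelet half is not.

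The participant at issue has marrow blasts below 5%, no other evidence of disease and a recovered ANC, but platelets at or below 100,000/µL without support. Under Table 7 that is CRi. Under the maximum-count rule, one transfused value above the level makes it CR. In the key EFS, tested at two-sided 0.01, the participant then moves from an event at time zero to a success followed for relapse or death. The same classification feeds the CR rate, which is in the fixed testing sequence of Section 9.4.3, and two of the three quantities in the first interim analysis (Section 9.5).

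**Working it through.** **1. The definitions side by side**

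| Item | Platelet level | Which count | Transfusion condition |
|---|---|---|---|
| CR for key EFS (9.4.2; Table 7) | >100,000/µL | Maximum within ±7 days of marrow (9.4.2) | None |
| Count recovery (Tables 1 and 2, footnotes) | >100,000/µL | Not specified | None |
| Platelet recovery (Table 7, Appendix 7) | >20,000, >50,000, >100,000/µL | First qualifying day | None given in preceding 5 days |

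The CR window is 7 + 1 + 7 = 15 days. With hematology every other day (Table 1), about 15/2, or 7 to 8, counts compete for the maximum.

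**2. The plan's own EFS figure.** Section 9.2 states more than 85% power with 454 events, HR 0.7 and two-sided alpha 0.01. By Schoenfeld's formula, √454/2 × |ln 0.7| − 2.576 = 3.800 − 2.576 = 1.224, so power = Φ(1.224) = 89.0%. The stated figure holds, and this point does not dispute it.

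**3. How many participants could move.** The documents give no frequency, so these are assumptions. At the planned 50% CR rate, 0.5 × 570 = 285 participants are failures at time zero.

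| Share of non-CRs reclassified | Participants moved | CR rate reads |
|---|---|---|
| 5% | 14 | 52.5% |
| 10% | 29 | 55% |
| 20% | 57 | 60% |

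A lower assumption of 1% to 3% of all 570 gives 6 to 17 participants, or 2% to 6% of the 285.

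**4. Effect on EFS.** Simulated unstratified log-rank test: 285 per arm, single analysis, two-sided 0.01, failures at time zero, assumed control median of 20 months after CR, and censoring uniform between 24 and 48 months. Where a post-CR effect is assumed, it is HR 0.7 from month 6. Reclassified participants are given the same post-CR course as other responders.

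- *No true effect, equal reclassification of 5% to 20% in both arms:* wins for dociparstat in 0.2% to 0.3% of 1,000 trials, against a nominal 0.5% in that direction. No inflation is seen.
- *True CR 50% versus 60%, equal reclassification (2,000 trials each):*

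| Reclassified | Average HR | Power |
|---|---|---|
| 0% | 0.73 | 62% |
| 5% | 0.73 | 64% |
| 10% | 0.74 | 60% |
| 20% | 0.75 | 58% |

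Simulation error on power is about 1 point (√(0.62 × 0.38/2,000) = 0.011), so only the 20% row departs clearly from the first. The 62% follows from the assumed scenario and is not comparable with the 89% in step 2.

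- *True CR 50% in both arms, equal reclassification:* the average HR goes from 0.86 to 0.85 at 20%. There is no CR difference to dilute.
- *No true effect, reclassification in the dociparstat arm only:* false wins of about 1.5%, 3% and 14% at 5%, 10% and 20%, against the nominal 0.5%. This is a bounding case; nothing in the documents supports it.

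**5. First interim.** With 80 evaluable participants at 1:1, about 40 per arm, one reclassified participant moves the CR difference by 1/40 = 2.5 points. If that participant is MRD-negative, CR with MRD negativity moves too, and the combined total shifts by 5 points.

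**6. Can the 5-day rule be applied with the planned data?** A marrow on Day 42 has a window ending on Day 42 + 7 = Day 49. Section 6.6 requires transfusion data only to 42 days after the start of the last cycle. For a participant with no further cycle, any marrow after Day 35 has a window running past the recorded data. Marrows on about Days 36 to 42 are the ones Table 1 calls for when counts have not recovered.

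**The case against.** **Transfusion does not create a remission.** A reader might infer that it does. CR still needs marrow blasts below 5%, no circulating blasts or Auer rods, no extramedullary disease and a recovered ANC. What can change is the grade of an existing remission, from CRi to CR. This stands.

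**The definitions do not contradict each other.** The 5-day condition belongs to an endpoint named as transfusion-independent, while CR is said to follow ELN 2017. Two endpoints may use different platelet rules. This stands too: the point is an improvement borrowed from the protocol's own rule, not an inconsistency that must be resolved.

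**Planned analyses already help.** EFS, RFS and relapse after CR/CRi, and the CR/CRi rate, count this participant as a responder either way. They are largely insensitive to the shift, though not wholly: a participant with both cytopenias is not CRi, and a transfused platelet count could remove one of them. They would help expose a problem but do not replace the alpha-controlled EFS. Consolidation is open to CR and CRi alike, so treatment does not depend on the distinction.

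**Bias by arm is not shown.** The trial is double-blind. Section 2.2 proposes an effect on platelet recovery, so transfusion use could differ by arm. If dociparstat reduced transfusions, however, the extra CRs might fall on placebo. The direction cannot be read from the documents, and they give no transfusion trigger or expected increment showing how often a transfused count would pass 100,000/µL.

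**The interim is not easily tipped.** Stopping requires the differences for CR, MRD negativity and CR with MRD negativity all to be below 5%, and MRD negativity regardless of CR does not depend on platelets. One participant in 40 is 2.5 points for any binary endpoint.

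**A separate SAP may cover it.** Section 9.4 defers technical detail there. The text available has no such rule, and the sentence in 9.4.2 reads as a complete instruction.

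**Conclusion.** The point holds as a cheap improvement to an endpoint definition. Followed as written, Section 9.4.2 and Table 7 allow a CRi to be classed as CR on a transfused platelet count, which changes a time-zero event into a success in the key secondary EFS. The CR endpoint and the CR components of the first interim share the exposure. OS does not.

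The likely effect is small. Reclassification that is equal between arms mainly dilutes a CR difference and showed no inflation of false wins. At an assumed 20% of non-CRs it cost about 4 points of power (62% to 58%) in the scenario with a true CR difference; at 5% to 10% the change was within or near simulation error. These results rest on assumed reclassification rates and an assumed post-CR course. The documents do not support the further inference that the key EFS result would be biased toward dociparstat: they give neither a frequency nor a difference between arms.

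**What to change.** 1. In Section 9.4.2 and the CR row of Table 7, state that, for deriving the CR endpoint, platelet counts within 5 days after a platelet transfusion are not used to determine count recovery. Carry the same wording into Appendix 7.
2. Close the data gap in one of two ways: record platelet transfusions to the end of the +7-day window (up to Day 49), or limit qualifying counts to the period with transfusion data.
3. Report the unrestricted maximum-count definition as a sensitivity analysis for the key EFS and the CR rate.
4. Settle this before the first interim analysis, by which time Section 9.4 says the SAP will be final.

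This changes the endpoint derivation only, not transfusion practice or any treatment decision. The cost is a sentence in each place, a slightly lower CR rate, and, under the first option in item 2, a few more days of transfusion data for participants with no further cycle.

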9.4.3. Other Secondary Endpoints

In the event that both the primary and key secondary analysis rejects the null hypothesis, the secondary analyses of MRD_{neg}, time to platelet recovery, time to neutrophil recovery, and CR will be tested in a fixed sequential manner at two-sided alpha 0.05. If the primary analysis rejects the null hypothesis while the key secondary does not, these secondary analyses will be tested in a fixed sequential manner at two-sided alpha 0.04; similarly, if the key secondary analysis rejects the null hypothesis while the primary analysis does not, these secondary analyses will be tested in a fixed sequential manner at two-sided alpha 0.01. No other multiplicity adjustments will be made for secondary analyses.

Time-to-event secondary analyses will use the same methods used for the primary and key secondary analyses.

Dichotomous secondary efficacy analyses will be analyzed using a Cochran-Mantel-Haenszel test stratified by each of the stratification factors. Number of successes/failures and success/failure rates will be presented for each treatment arm. Cochran-Mantel-Haenszel p-values, estimated common odds ratios, and corresponding approximate 95% CIs will be presented for each comparison. The Breslow-Day test will be used to test the homogeneity of the odds ratios across the strata. Missing data will generally be imputed as failure unless specifically defined otherwise in the SAP.

Cumulative incidence of relapse will be analyzed with death as a competing risk adjusted for baseline strata, with corresponding cumulative incidence plots, Fine-Gray models, and cause-specific and sub distribution hazard ratios with corresponding 95% CIs.

OS, EFS, and MRD will be analyzed by various subgroups, including, but not limited to, each of the stratification factors, anthracycline use, sex, and race (each race contributing >10% to the study plus other races grouped). OS and relapse will be analyzed by number of consolidation cycles. Multivariate modelling to assess the impact of these factors on key endpoints will be considered and defined in the SAP.

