1.2. Schedule of Activities

Table 1: Schedule of Activities/Assessments: Induction Cycle and Reinduction Cycle (as applicable)

Study Day:	Screen ^a	BL/ D1	D 2	D 3	D 4	D 5	D 6	D 7	D 8	D 14- 21	D22 until count recovery or Day 42 ^c	Post-CR	Early Therapy DC	Notes
Examination / Procedure														Study day is relative to start of each treatment cycle
Informed consent	X													
Eligibility criteria	X	X												
Demographics	X													
Medical history	X	X												
ECOG status (induction only)	X	X												
Physical exam and vital signs	X													Predose findings=medical history; Findings after first dose=AE
Height / Weight	X													
ECG (induction only)	X	X							X					D1: Before and after bolus dose; D8: At the end of infusion
Echocardiogram / MUGA scan	X													Repeat per standard of care.
Pregnancy test (as applicable)		X												Women of childbearing potential
Peripheral blood samples:														
– Molecular genetics (central)	X													
– Immunophenotyping (central)	X													
– FISH (central)	X													
– Fibrinogen, D-dimer (local)	X													
– Clinical chemistry (local)	X	X	X		X		X		X	D14				
– Hematology (local)	X	X	X		X		X		X	X	X			Every other day through recovery.
– PT/INR, aPTTe,f (local)	X	X ^f	X	X	X	X	X	X	X	D14				Do not draw from the same line used for drug administration ^e
– PK blood samples ^e (central) (induction only) (at sites with appropriate capabilities)		X			X				X					(±10min) D1: predose, end of bolus, and 1 and 12 hours after bolus; D4: morning; D8: end of infusion, and 0.5, 1, 2, and 4 hours after end of infusion
– HMGB1 ^{e,g} (central)		X			X				X	D14	At recovery ^{b,c}			
– Biobanking (central)	X										X ^c			Optional, per local regulation/approval

Consolidation Therapy, as applicable – see Table 2

Study Day:	Screen ^a	BL/ D1	D 2	D 3	D 4	D 5	D 6	D 7	D 8	D 14- 21	D22 until count recovery or Day 42 ^c	Post-CR	Early Therapy DC	Notes
Examination / Procedure													Study day is relative to start of each treatment cycle	
Bone marrow aspirate/ biopsy:														
– MRD analyses (central)	X										At recovery ^{b,c}			Required. Use first draw of marrow.
– Biobanking (central)	X										At recovery ^{b,c}			Optional, per local regulation/approval
– Morphology (local)	X									X ^b	At recovery ^{b,c}			
– Cytogenetics (local)	X													
Buccal swab or saliva specimen (central) (induction only)											X			Optional, single sample for germ line analysis

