9.4.1. Primary Endpoint

The primary OS inferential analysis will utilize the ITT analysis set and a log-rank test at two-sided alpha 0.04 stratified by baseline FLT3 status, cytogenetic risk, and age. Kaplan-Meier (KM) methods/plots and Cox models will be used. Log-rank p-values and hazard ratios with 95% CIs will be presented for each treatment comparison. Median failure times, KM estimates every 90 days, and corresponding 95% CIs will be presented for each group. Survival time will be measured from randomization. Participants who are not known to have died will be censored at the time they were last known to be alive. The final primary analysis will be conducted after approximately 308 death events have been observed.

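### Time to platelet and neutrophil recovery inherit the survival method with no rule for death before recovery, so the Kaplan-Meier recovery estimates would overstate the proportion recovering

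*Combined protocol and SAP*

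**What the plan says.** Section 9.4.3 tests MRD negativity first and then, in order, "time to platelet recovery, time to neutrophil recovery, and CR will be tested in a fixed sequential manner at two-sided alpha 0.05" (0.04 or 0.01 if only OS or only EFS rejects). On method it says "Time-to-event secondary analyses will use the same methods used for the primary and key secondary analyses". Recovery is not excepted.

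The method referred to is in Section 9.4.1:
- the test is "a log-rank test at two-sided alpha 0.04 stratified by baseline FLT3 status, cytogenetic risk, and age";
- for estimation, "Kaplan-Meier (KM) methods/plots and Cox models will be used";
- for reporting, "Median failure times, KM estimates every 90 days, and corresponding 95% CIs will be presented for each group";
- for censoring, "Participants who are not known to have died will be censored at the time they were last known to be alive".

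Section 9.4.2 (EFS) uses the same test and adds a rule that imputes induction failure at randomization. That rule has no counterpart for count recovery.

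The recovery endpoints are defined for all participants, from randomization to the first day above the threshold (Section 8.2.2, Table 7; Appendix 7). Neither place gives a rule for death before recovery, for survivors who never recover, or for the end of count assessment.

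Relapse is treated differently: "Cumulative incidence of relapse will be analyzed with death as a competing risk adjusted for baseline strata", with Fine-Gray models and both kinds of hazard ratio. Table 7 also counts deaths without relapse as competing events.

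In Table 1 (Section 1.2) the late assessment column is "D22 until count recovery or Day 42", counted from the start of each treatment cycle.

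**The concern.** Death before recovery is a real possibility here; Day 30 and Day 60 mortality are safety endpoints. A participant who dies without recovering can never recover. If the survival method is applied to recovery as it stands, the only way such a participant leaves the risk set is by censoring at death. Kaplan-Meier then treats the participant as someone who would later have recovered at the same rate as those still under observation. One minus Kaplan-Meier no longer estimates the proportion of randomized participants who recover. It also does not respond to a difference in early death between arms.

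Two smaller mismatches come with the inherited rule. The first 90-day estimate comes after the recovery period is essentially over. And survivors who have not recovered would be kept at risk until last known alive, possibly years after scheduled counts stopped.

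At stake is the meaning of the recovery rates and medians reported beside two tests in the controlled sequence.

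**Working it through.** **1. The plan's own figures.** The documents give no rate, power or sample size for the recovery endpoints, so there is no recovery figure to reproduce. The figures used below for scale are the OS assumptions in Section 9.2: control median 18 months and HR 0.7. The stated dociparstat median reproduces: 18 / 0.7 = 25.7 months.

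**2. Early death implied by those medians.** If survival is exponential, the probability of death by day d is 1 − exp(−ln 2 × (d / 30.4375) / median). At Day 60:
- control: 7.3%;
- dociparstat: 5.2%.

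This is only a scale marker. Deaths concentrated in induction would give more.

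**3. Assumptions for the recovery check (none from the documents).** A fraction q of 60% to 90% is able to recover. Their recovery day R is lognormal with median 32 and sigma 0.25. The death hazard λ is constant, with 2% to 15% dead by Day 60, so λ = −ln(1 − p) / 60.

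**4. Formulas.**
- With deaths censored, one minus Kaplan-Meier at day t tends to q × P(R ≤ t).
- Cumulative incidence with death competing is q × E[exp(−λR); R ≤ t].

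By Day 90 almost all of R has passed. The first is then close to q and the second close to q × exp(−λ × mean R), where mean R = 32 × exp(0.25² / 2) = 33.0 days.

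**5. Worked example, q = 75%, p = 10%.** λ = −ln(0.90) / 60 = 0.001756 per day. exp(−0.001756 × 33.0) = 0.944. Cumulative incidence = 0.75 × 0.944 = 0.708, against 0.750. The overstatement is 4.2 points. Simulation with 1,000,000 participants gave the same 0.750 and 0.708.

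**6. Range.** Simulated overstatement at Day 90, in percentage points:

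| Able to recover | 2% dead by Day 60 | 5% | 10% | 15% |
|---|---|---|---|---|
| 60% | 0.6 | 1.6 | 3.4 | 5.1 |
| 75% | 0.8 | 2.1 | 4.2 | 6.3 |
| 90% | 1.0 | 2.5 | 5.1 | 7.7 |

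The median moved by 0 to 4 days; the largest shift was Day 41 against Day 45, at 60% and 15%.

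**7. At the plan's own early-death scale, q = 75%.**
- Control: λ = ln 2 / (18 × 30.4375) = 0.001265; 0.75 × exp(−0.001265 × 33.0) = 0.719, an overstatement of 3.1 points.
- Dociparstat: λ = ln 2 / (25.7 × 30.4375) = 0.000886; 0.75 × exp(−0.000886 × 33.0) = 0.728, an overstatement of 2.2 points.

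One minus Kaplan-Meier is 0.750 in both arms, so it does not show the 0.9-point difference in the proportion recovering.

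**8. The test.** Equal recovery hazards, 285 per arm, 2,000 runs, unstratified log-rank at two-sided 5%:

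| Dead by Day 60, arm 1 v arm 2 | Deaths censored | Deaths kept at risk as unrecovered |
|---|---|---|
| 5% v 5% | 4.6% | 4.8% |
| 10% v 10% | 4.9% | 4.6% |
| 10% v 5% | 4.1% | 7.9% |
| 15% v 5% | 5.1% | 17.7% |
| 5% v 10% | 5.1% | 8.1% |

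With deaths censored the test keeps its size. The last column rejects more often when early death differs because it targets cumulative incidence, which does differ between the arms.

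**9. Time axis.** Recovery is counted from randomization. Reinduction can follow the marrow at Day 14 to 23 or the response assessment at about Day 22 to 42 (Section 4.3). Day 42 of a reinduction cycle therefore falls at roughly Day 14 + 42 = 56 to Day 42 + 42 = 84. Scheduled recovery assessment is essentially complete before the first 90-day estimate, but for reinduced participants it is not complete at Day 42.

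**The case against.** **Censoring of deaths is not written down for recovery.** The censoring sentence in Section 9.4.1 is about participants not known to have died, and read literally it is silent on someone who dies before recovering. Section 9.4 calls itself a summary and leaves detail to the SAP; the text available contains no such detail for recovery. This stands. A reader might infer that the plan prescribes censoring of deaths. What the documents support is that handling is unspecified, that the only method named would in effect censor them, and that this is out of line with the relapse analysis.

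**The controlled result is the log-rank.** A reader might infer that two alpha-controlled tests are biased or inflated. The documents and the check do not support that: the test is valid for the cause-specific recovery hazard, with 4.1% to 5.1% rejection at a nominal 5%. This stands in full.

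**Count collection does not stop at Day 42 for everyone.** Correct. Table 1 days restart with each cycle, so reporting days ending at Day 42 from randomization would miss many reinduction recoveries.

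**The grid is a presentation choice.** Kaplan-Meier plots and medians do describe the early weeks, so the 90-day grid alone is minor. But the plots and medians carry the same overstatement.

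**An imbalance would show elsewhere.** Early mortality and prolonged cytopenia are reported separately, and the recovery tests are reached only after OS or EFS and then MRD negativity succeed. That limits the consequences; it does not make the recovery estimates right.

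**Conclusion.** The point holds for estimation. Following Section 9.4.3 as written gives Kaplan-Meier recovery estimates that exceed the proportion recovering whenever deaths precede recovery. The excess is 0.6 to 7.7 points at Day 90 over an assumed 2% to 15% dead by Day 60 and 60% to 90% able to recover. It is 2 to 3 points at the early-death level implied by the plan's OS medians with 75% able to recover. Medians move by 0 to 4 days. These sizes rest on assumed recovery times and a constant death hazard, and they concern within-arm levels.

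The point does not extend to the hypothesis tests: no type I error inflation is shown, and no bias in the cause-specific comparison. It is a low-priority but cheap correction, and it is already met if the SAP specifies competing-risk handling for recovery.

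**What to change.** For time to platelet recovery and time to neutrophil recovery, add to Section 9.4.3 and the SAP:
- Replace one minus Kaplan-Meier with cumulative incidence, treating death before recovery as a competing event, and take medians from that curve.
- Censor survivors without recovery at their last count assessment, not at last known alive.
- Report at days from randomization that cover both induction and reinduction, for example Days 28, 42, 56, 70 and 84, in place of every 90 days.
- Keep the stratified log-rank as the alpha-controlled test, stated as a test of the cause-specific recovery hazard, and add a supportive Fine-Gray model.

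The cost is a few sentences and a little more programming, using methods already planned for relapse. Reported recovery rates will be slightly lower. The testing sequence, alpha and sample size do not change.
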